**Document date: Thursday December 12, 2024**

## Research Approach

We will achieve our aims by having 200 non-smoking adolescents (aged 15-16) complete a laboratory study (Figure 2). During their visit, Adolescents will then be randomly assigned to watch a smoking movie that manipulates exposure to ENDS Advertisements. Attention to movie smoking will be measured using validated eye movement measures of attention. Adolescents will then complete SC-IAT task to measure how exposure to ENDS ads affected their implicit smoking expectancies and implicit normative beliefs.

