## Primary Measures

**Implicit measurement of positive smoking expectancies and social normative beliefs about smoking using the SC-IAT.** A modified version of the SC-IAT will be administered before and after exposure to ENDS ads. The SC-IAT is a validated implicit association computer task that can be used to measure the associations between a visual cue (e.g., a smoking-related image) and a) personal implicit attitudes (e.g., implicit positive smoking expectancies)

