and b) implicit normative evaluations (e.g., social normative beliefs about smoking). The rationale for using the implicit association tests to assess implicit attitudes and implicit normative evaluations have been described elsewhere. Adolescents will complete two phases, a personalized phase to measure their implicit positive smoking expectancies and a social phase to measure their implicit normative beliefs about smoking (Figure 3). Each trial in the personalized phase begins with the words “Things you find positive or negative ...” presented in the upper middle of the screen that stays visible for the duration of the trial. After 500 msec, adolescents are presented with a visual smoking cue and associated word or short phrase presented in the middle of the screen. The word either conveys a positive smoking expectancy (e.g., relaxation) or a negative smoking expectancy (e.g., bad mood). The labels “Positive” and ‘Negative’ are presented on opposite sides at the top right-hand and left-hand side of the screen. The task of the participant is to categorize the cue word as “positive” or “negative” by pressing the spatially-mapped keyboard key as quickly and accurately as possible. The theory is that participants will categorize the word faster if the visual cue word pairing is congruent with their smoking expectancies. For example, an individual with high positive smoking expectancies would react faster if a visual smoking cue was paired with a positive word, such as “relaxation” than a negative word, such as “bad mood.” In a control condition, neutral non-smoking images are presented instead of smoking images. Trials in the social phase are like the personalized phase with the following expectations. Trials begin with the wording “Things most people find positive or negative ...” followed by the presentation of the trial screen. The cue word will convey a positive (cool) or negative (uncool) social belief about smoking. Like above, the theory is that participants will categorize the word faster if the visual cue word pairing is congruent with their social normative beliefs about smoking. The order in which phases are completed will be counterbalanced, and experimental procedures will follow established methods. Visual smoking images and control images will be taken from the International Smoking Image database. Smoking-related images include photos of people smoking in a variety of environmental situations. Neutral images are identical but have the smoking cues removed. Positive and negative cue words will be sampled from previous research that have used similar tasks. and derived from scales that measure smoking expectancies and normative smoking beliefs designed for adolescents.

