
**ENDS ad and control exposure.** Immediately following the first SC-IAT,

adolescents will view a 15-minute movie clip that manipulates exposure to ENDS ads. ENDS ad exposure will be manipulated by embedding naturally occurring commercial breaks at 5 and 10 minutes. During each break, adolescents in the ENDS ad exposure condition will view ENDS ads for 30 seconds each. The commercial break will also include 3 30-sec control ads (e.g., food, clothes, and cars) to disguise the purpose of the experiment. Adolescents in the control ad condition will view 4 minutes of control commercials at each break. ENDS and control ads will be randomly sampled from the 8 most popular brands in the United States in 2016.

**Attention to dynamic smoking cues.** Dynamic smoking cues are any action that promotes or represents a smoking behavior. Selective attention is an implicit measure of cue saliency that is defined as an automatic response to attend to an environmental stimulus. Measuring eye movements to dynamic cues has been shown to be a validated measure of selective attention to smoking cues in movies. Eye tracking will be recorded using the Gazepoint GP3 eye-tracker (Vancouver, British Columbia). The GP3 device has a sample rate of 60 Hz and an accuracy of 0.5 to 1 degree of visual angle.

**Covariate Assessment.** We will measure the following covariates because they have been associated with tobacco advertising exposure and adolescent smoking, but are not thought to part of the causal pathway. We will collect sociodemographic factors including age, gender, and socioeconomic status. Socioeconomic status will be measured using the validated three item index of the Programme for International Student Assessment. We will also measure social influences on smoking using validated questions, including the smoking status of parents and the smoking status of peers. Rebelliousness and sensation seeking will be assessed using a validated 4-item index because it has been strongly associated with adolescent smoking intuition. Following our laboratory's previous work, we will also measure long-term exposure to on screen movie smoking using a validated method.

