## Primary analysis plan

Our outcomes of interest are as follows: 1) Implicit positive vaping expectancy scores measured post-intervention, and 2) selective attention to dynamic smoking cues. To assess the effect of ENDS advertising on implicit attitudes, we will use linear regression to predict Implicit positive vaping expectancy scores from advertising condition. We also use linear regression to assess the association between the amount of attention given to dynamic smoking cues and Implicit positive vaping expectancy scores. Specially, Implicit positive vaping expectancy scores will be predicted from dynamic attention scores in the onscreen smoking experimental arm. For all analyses, we will first calculate appropriate summary statistics, assess normality, and transform the data if necessary. We will include potential covariates in all analyses when they are significantly associated with the outcome ( $P < 0.05$ ). We will conduct all analyses in the full sample stratified by sex, and conduct formal tests for interactions using a Wald Test on sex by exposure multiplicative interaction terms in full models.

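### The pre-exposure SC-IAT score is collected but is not a pre-specified covariate in either expectancy regression

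*Combined protocol and SAP*

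**What the plan says.** Under Primary Measures, the SC-IAT "will be administered before and after exposure to ENDS ads", and the movie clip starts "Immediately following the first SC-IAT". A pre-exposure score is therefore collected, including one from "a personalized phase to measure their implicit positive smoking expectancies".

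The Primary analysis plan defines the first outcome as "Implicit positive vaping expectancy scores measured post-intervention". For the advertising effect, "we will use linear regression to predict Implicit positive vaping expectancy scores from advertising condition". A second linear regression predicts the same score from dynamic attention, within an experimental arm that is identified by onscreen smoking. No change score, baseline-adjusted model or repeated-measures model is described.

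Other variables enter through one rule that covers all analyses: potential covariates are included when associated with the outcome at P<0.05. The Covariate Assessment paragraph begins "We will measure the following covariates because they have been associated with tobacco advertising exposure and adolescent smoking". It then lists age, gender, socioeconomic status, parent and peer smoking, rebelliousness and sensation seeking, and long-term exposure to movie smoking. The pre-exposure SC-IAT score is not on that list. All analyses are also to be stratified by sex.

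**The concern.** Nothing in the document says what the first SC-IAT is for in the analysis. If the screen applies only to the listed covariates, baseline is left out. If it is read more widely, the data decide whether baseline enters. The wording of the Covariate Assessment paragraph leans towards the first reading but does not settle it. On neither reading is baseline pre-specified.

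The two regressions are affected differently. Advertising condition is randomised, so leaving baseline out costs precision only. Attention is observed. An adolescent who already holds positive expectancies may look more at smoking cues and also score higher afterwards, and the pre-exposure score is the direct measure of that confounder. Without it, the slope describes a marginal association and cannot be read as a relation beyond baseline.

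Two wording problems stand in the way of a simple repair. Primary Measures describes smoking expectancies, whereas the analysis plan models vaping expectancies. The arm named for the attention analysis also matches neither advertising condition: Research Approach says "Adolescents will then be randomly assigned to watch a smoking movie that manipulates exposure to ENDS Advertisements", so all participants see a smoking movie, and the conditions differ only in the ads (for example, "Adolescents in the control ad condition will view 4 minutes of control commercials at each break").

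**Working it through.** **Inputs.** From the document: 200 participants, random assignment, SC-IAT before and after, covariate screen at P<0.05. There is no power calculation to reproduce; no effect size, SD, allocation ratio or correlation is given. Assumed here: 100 per arm, two-sided 0.05, 80% power, SD 1, and the correlations shown. Write r for the baseline-post correlation and a for the baseline-attention correlation.

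**1. Arm comparison, baseline left out.** The normal approximation gives (1.960 + 0.842) × √(2/100) = 0.396 SD; the noncentral t gives 0.398. Adjusting for baseline multiplies the error variance by (1 − r²), and the equivalent total sample is 200/(1 − r²).

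| r | Detectable difference with baseline | Equivalent N |
|---|---|---|
| 0.3 | 0.380 | 200/0.91 = 220 |
| 0.5 | 0.345 | 200/0.75 = 267 |
| 0.7 | 0.284 | 200/0.51 = 392 |

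Suppose the listed covariates are in the model, explain 10% of the post score (correlation 0.316) and correlate 0.4 with baseline. The partial correlation is then (r − 0.316 × 0.4)/√(0.90 × 0.84) = 0.200, 0.430 and 0.660, and the equivalent N is 208, 245 and 354.

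**2. Attention regression, baseline left out.** If attention has no effect given baseline, the marginal attention-post correlation is a × r. The probability of P<0.05 is Φ(m − 1.96) + Φ(−m − 1.96), with m = atanh(a × r) × √(n − 3). For a = 0.4, r = 0.7 and n = 100: m = atanh(0.28) × √97 = 2.83, giving 0.81.

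| r (n = 100) | a = 0.1 | a = 0.2 | a = 0.3 | a = 0.4 |
|---|---|---|---|---|
| 0.3 | 0.060 | 0.091 | 0.144 | 0.221 |
| 0.5 | 0.078 | 0.167 | 0.319 | 0.515 |
| 0.7 | 0.106 | 0.284 | 0.555 | 0.809 |

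If the analysis set is all 200, the range is 0.071 to 0.981. With the listed-covariate composite of step 1 in the model, related to attention only through baseline, the range at n = 100 is 0.054 to 0.688.

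**3. Screen admits baseline.** By simulation at n = 100, baseline enters 86.5% of the time at r = 0.3 and more than 99.9% at r = 0.5 or 0.7. Rejection in the attention model after the screen is 0.049 to 0.054 over the same twelve cells. At n = 200 and r = 0.3, the Fisher z formula gives entry 99.1% of the time.

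If the screen is re-run within each sex, with equal numbers, the probability that baseline is kept in one sex and dropped in the other is 2p(1 − p), where p is the entry probability.

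| Model | p at r = 0.3 | Discordance | p at r = 0.5 | Discordance |
|---|---|---|---|---|
| Attention, 50 per sex | 0.570 | 49% | 0.967 | 6% |
| Arm comparison, 100 per sex | 0.865 | 23% | 0.9998 | under 0.1% |

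**4. Limit of the adjustment.** The 5% in step 3 assumes that the observed baseline score carries all the confounding. Suppose instead that a stable latent expectancy drives attention and both scores, with reliability 0.5, pre-post r = 0.5 and a = 0.3. The attention-post correlation is then 0.30. Given baseline it is (0.30 − 0.50 × 0.30)/√(0.75 × 0.91) = 0.18. Simulated rejection at n = 100 is 0.867 unadjusted and 0.439 adjusted.

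**The case against.** The strongest reply is that little is broken. A post-score regression on a randomised condition is a legitimate, unbiased analysis, and the plan makes no power claim that it then misses. This stands: for the arm comparison, baseline adjustment is an improvement and not the repair of an error.

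Second, the large attention figures need both a sizeable r and a screen that excludes baseline. The SC-IAT is already described as a primary measure, so its absence from a list of additional items to collect is weak evidence that it is excluded. If it is a candidate, it will nearly always enter at r of 0.5 or more. This also stands, and it is why the high figures apply to one reading only.

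Third, the document gives no correlation, so r could be below 0.3. At r = 0.2 the equivalent N is 200/0.96 = 208, and attention rejection at n = 100 is about 5% to 12%. The gain is then small.

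Fourth, the plan speaks of an association, and in these scenarios a marginal association does exist. The rejection rates are therefore error rates only for a claim beyond baseline, not for the analysis as literally worded.

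Finally, the composite in steps 1 and 2 is a single assumed case, and the plan does not say that the screen is re-run by sex. Both are fair limits on those particular numbers. None of these points supplies the missing statement of how the pre-exposure score is used.

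**Conclusion.** The concern holds as a should-fix point, with medium confidence. The gap in the text is certain; its size depends on correlations that the document does not give.

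- **Arm comparison:** validity is not in question. If baseline is left out, the trial forgoes precision worth about 20 to 192 extra participants at r of 0.3 to 0.7 (220 − 200 to 392 − 200), and about 8 at r = 0.2.
- **Attention regression:** this is where the omission matters most. If baseline is left out, a significant slope cannot be separated from expectancy that existed before the movie.
- **Screen admits baseline:** at r of 0.3 or more both problems largely disappear. What remains is adjustment that depends on the data and, if the screen is re-run by sex, may differ between the strata.

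Even fixed adjustment would not remove confounding that an imperfectly measured baseline fails to capture.

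**What to change.** 1. Reconcile the smoking wording in Primary Measures with the vaping wording in the Primary analysis plan, so that the pre and post scores are the same measure.
2. Reconcile the arm named for the attention analysis with the two advertising conditions, and state the analysis set.
3. Pre-specify the personalized-phase pre-exposure score as a fixed covariate in both expectancy regressions and in both sex strata, exempt from the P<0.05 screen. Do this before outcome data are seen.
4. Report the attention result as an association given baseline, and note that SC-IAT measurement error may leave residual confounding.

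Once items 1 and 2 are settled, this is a short edit to the analysis plan. It costs one degree of freedom per model and needs no new data.

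### The attention regression names an arm that the design does not contain; unless it means control-ad viewers only, its slope can partly reflect watching the ENDS ads in the same clip

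*Combined protocol and SAP*

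**What the plan says.** The combined protocol and SAP describes one randomised factor. In Research Approach, adolescents are "randomly assigned to watch a smoking movie that manipulates exposure to ENDS Advertisements". Both conditions therefore see movie smoking, and only the advertisements differ.

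Primary Measures puts the ads inside the film clip: "ENDS ad exposure will be manipulated by embedding naturally occurring commercial breaks at 5 and 10 minutes". During the breaks, "adolescents in the ENDS ad exposure condition will view ENDS ads for 30 seconds each". On gaze it says "Eye tracking will be recorded using the Gazepoint GP3 eye-tracker", without saying whether recording runs through the breaks. A cue is defined broadly: "Dynamic smoking cues are any action that promotes or represents a smoking behavior".

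The Primary analysis plan has two regressions. The first compares the expectancy score between advertising conditions. The second is the one at issue: "We also use linear regression to assess the association between the amount of attention given to dynamic smoking cues and Implicit positive vaping expectancy scores". Its population is given as follows: the expectancy score "will be predicted from dynamic attention scores in the onscreen smoking experimental arm". Apart from covariates that pass a P < 0.05 screen against the outcome, attention is the only predictor named. The candidate covariates in Primary Measures are age, gender, socioeconomic status, parental and peer smoking, rebelliousness and sensation seeking, and long-term exposure to movie smoking. Neither advertising condition nor gaze on the ads is among the terms named for this model.

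**The concern.** An adolescent in the ENDS-ad condition sees movie smoking and ENDS ads in one sitting, and the post-exposure expectancy score follows both. The trial's premise is that the ads shift that score. It is plausible that someone who watches the screen closely, or whose eyes go to nicotine cues, looks more at both. Gaze on the ads would then be a second cause of the outcome, correlated with the predictor and absent from the model.

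Randomisation does not protect this slope, because attention is not randomised and gaze on the ads varies among those shown them. If the two conditions are pooled, there is a further route. Attention to smoking cues is itself listed as an outcome, so advertising condition may move both sides of the regression.

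What is at stake is attribution. A positive slope would invite the reader to credit on-screen smoking, yet the same slope could arise if only the ads mattered.

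**Working it through.** **Which participants?** The undefined arm has three possible readings.

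- ENDS-ad condition: ads and movie smoking are both seen, so the problem is present.
- Whole sample: the problem is present in the part that saw ENDS ads, and advertising condition is missing from the stated model.
- Control-ad condition: no ENDS ads are seen, so the problem is absent.

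**Inputs from the documents.** Total sample: "We will achieve our aims by having 200 non-smoking adolescents (aged 15-16) complete a laboratory study". No effect size, standard deviation, power or allocation ratio is given, so there is no stated figure to reproduce.

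**Assumed inputs.** Equal allocation, hence 200 / 2 = 100 per condition; two-sided 5% test; no true effect of attention to movie smoking; standardised effect β of ad gaze on expectancy, 0.2 to 0.4; correlation ρ between the two gaze measures, 0 to 0.6.

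**Formula.** With ad gaze omitted, attention and expectancy have a spurious correlation r = β × ρ. By Fisher's z, the test statistic is centred at m = atanh(r) × √(n − 3), and the rejection probability is Φ(m − 1.96) + Φ(−m − 1.96).

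**Worked case, n = 100, β = 0.3, ρ = 0.4.** r = 0.3 × 0.4 = 0.12; atanh(0.12) = 0.1206; √97 = 9.849; m = 1.188. Rejection = Φ(−0.772) + Φ(−3.148) = 0.220 + 0.001 = 0.221.

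**Rejection rate over the range, n = 100:**

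| β | ρ = 0 | ρ = 0.2 | ρ = 0.4 | ρ = 0.6 |
|---|---|---|---|---|
| 0.2 | 5% | 7% | 12% | 22% |
| 0.3 | 5% | 9% | 22% | 43% |
| 0.4 | 5% | 12% | 36% | 67% |

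The spurious slope runs from 0.2 × 0.2 = 0.04 to 0.4 × 0.6 = 0.24. A least-squares simulation (3,000 replicates) agrees, with 9%, 22% and 68% for (β, ρ) = (0.3, 0.2), (0.3, 0.4) and (0.4, 0.6).

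**Both conditions pooled, n = 200, half seeing ENDS ads.** The spurious slope halves to 0.03, 0.06 and 0.12 for the same three pairs, and the simulated rejection rates are 8%, 14% and 43%. This simulation lets advertising condition change neither mean attention nor mean expectancy. If it changes both, the pooled model carries additional bias that these rates do not include.

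**Does adding ad gaze cure it?** If ad gaze is the only common cause, yes: simulated rejection returns to about 4% to 6%. If a trait drives both gaze measures and also raises expectancy directly (standardised 0.2 to 0.3, assumed), it does not. At n = 100 and with ad gaze in the model, rejection was about 14% to 30% for (ρ, β) = (0.5, 0.3) and about 13% to 25% for (0.3, 0.2).

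**Precision of a within-condition slope.** With 80% power, the detectable correlation is tanh((1.96 + 0.84) / √(n − 3)): about 0.28 for n = 100 and 0.20 for n = 200.

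**The case against.** The strongest reply is that the plan claims only an association. Under the assumed inputs attention and expectancy really are correlated, so rejecting is not an error for an association. That stands. The rates above are false-positive rates only for a reader who takes the slope as an effect of movie smoking, and the plan does not say that it will be read so. It remains true that the slope cannot show which of two exposures in the same clip it reflects.

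A reader might go further and infer that the plan wrongly leaves out a covariate that should be forced into the main model. The documents do not support that, for four reasons.

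- They do not say that gaze is recorded during the breaks. That is an inference from the ads being embedded in the clip.
- Attention in the first 5 minutes precedes any ad, so ad gaze may lie downstream of it. The plan chooses covariates thought to be off the causal pathway.
- If ads fill the screen, the share of ad time with valid gaze may be near ceiling and mostly measure tracking loss.
- The cue definition is wide enough that ENDS ads might already count in the attention score, although Research Approach speaks of attention to movie smoking.

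A reader might also infer that adding ad gaze restores a 5% error rate. That holds only if ad gaze is the sole common cause, as the trait simulation shows.

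**Conclusion.** The concern holds in a limited form. The population of the attention regression is undefined. On two of its three readings the slope cannot separate movie smoking from ENDS ads watched in the same session; on the third, control-ad viewers only, the question does not arise.

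The bias is zero if the two gaze measures are uncorrelated. Over the assumed range at n = 100, the rate of wrongly finding a movie-smoking effect is about 7% to 68%, with lower rates in the pooled simulation. All of this rests on assumed values of ρ and β and on a causal reading of the slope, so it shows what could happen and does not estimate what will.

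The randomised comparison of advertising conditions is unaffected, and nothing here suggests that it is biased.

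**What to change.** In the Primary analysis plan:

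1. Replace the undefined arm with the two randomised conditions. Fit the attention–expectancy regression separately in the control-ad and ENDS-ad conditions, and include advertising condition in any pooled model.
2. Name the control-ad slope as the estimate that ENDS ads in the session cannot explain. It remains observational, since attention is not randomised and a shared trait could still contribute.
3. State that the attention score excludes footage from the ad breaks.
4. If gaze is recorded during the breaks, report as a sensitivity analysis only the ENDS-ad slope with the share of ENDS-ad time spent looking at the ads added. State that this share may be near ceiling, may partly lie downstream of attention in the first 5 minutes, and reduces the bias without necessarily removing it.

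**Cost.** Revised wording and some extra scoring of the gaze recording, with no extra visit or participant. The main price is precision: with about 100 per condition, each slope has 80% power only for a correlation of about 0.28, against 0.20 for all 200. In the sensitivity model, collinearity inflates the variance of the attention slope by 1/(1 − ρ²), which is 1/0.96 = 1.04 at ρ = 0.2 and 1/0.64 = 1.56 at ρ = 0.6.

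### The attention–expectancy regression is set in an arm whose label matches neither advertising condition in the available text, so its analysis population cannot be identified

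*Combined protocol and SAP*

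**What the plan says.** The Research Approach section plans for 200 adolescents and describes the allocation thus: "Adolescents will then be randomly assigned to watch a smoking movie that manipulates exposure to ENDS Advertisements". It then says "Attention to movie smoking will be measured using validated eye movement measures of attention", with no restriction to one group.

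The Primary Measures section, under ENDS ad and control exposure, describes two conditions. For one: "During each break, adolescents in the ENDS ad exposure condition will view ENDS ads for 30 seconds each". For the other: "Adolescents in the control ad condition will view 4 minutes of control commercials at each break". The clip is described as varying the ads. On-screen smoking is not described as varying between groups.

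The Primary analysis plan specifies two regressions. The first predicts the expectancy score from advertising condition. The second relates attention to expectancy: "Implicit positive vaping expectancy scores will be predicted from dynamic attention scores in the onscreen smoking experimental arm". Two general rules follow:

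- on covariates, "We will include potential covariates in all analyses when they are significantly associated with the outcome", at P < 0.05;
- on the sample, "We will conduct all analyses in the full sample stratified by sex".

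**The concern.** The label in the second regression does not correspond to either condition. Both ad groups are described as watching a smoking movie, so on-screen smoking does not tell them apart. An analyst could defend the ENDS ad arm, the control ad arm or both combined, and could make that choice after seeing the results. This is one of only two regressions spelled out in the primary plan.

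The choice has consequences. A one-arm analysis loses precision. A two-arm analysis keeps everyone, but raises the question whether advertising condition is in the model. Condition is absent from the covariate list (age, gender, socioeconomic status, parental and peer smoking, rebelliousness and sensation seeking, long-term exposure to movie smoking). The plan does not say whether it is a candidate under the P < 0.05 rule.

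**Working it through.** The plan gives no power calculation for this association, so there is no figure of its own to reproduce.

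**Step 1. Set the labels side by side.**

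| Place | How the groups are identified |
|---|---|
| Research Approach | by ENDS ad exposure, within a smoking movie |
| Primary Measures | ENDS ad condition; control ad condition |
| Primary analysis plan, first regression | advertising condition |
| Primary analysis plan, second regression | an on-screen smoking arm |

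The last label appears nowhere else in the available text. On-screen smoking appears otherwise only as content of the movie and, as long-term exposure, as a measured covariate.

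**Step 2. Reading 1: one ad arm.** The only input from the documents is n = 200. Assumed: all 200 have usable eye-tracking, 1:1 allocation, a common slope, two-sided alpha 0.05, 80% power. With the Fisher-z approximation, detectable r = tanh((1.960 + 0.842)/sqrt(n − 3)).

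- n = 200: tanh(2.802/sqrt(197)) = 0.197
- n = 100: tanh(2.802/sqrt(97)) = 0.277
- If allocation were 2:1, the single arm would hold 133 or 67: 0.241 or 0.337

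Power at a true r of 0.20 is Phi(atanh(0.20) × sqrt(n − 3) − 1.960), with atanh(0.20) = 0.2027.

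- n = 200: Phi(2.845 − 1.960) = 0.812
- n = 100: Phi(1.997 − 1.960) = 0.515

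**Step 3. Reading 2: everyone who saw the movie.** Nobody is lost. Suppose the true within-arm slope is zero, both variables have unit SD within arms, and the ads shift each by d. With 1:1 allocation and condition omitted, the pooled correlation is (d²/4)/(1 + d²/4).

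- d = 0.3: 0.0225/1.0225 = 0.022
- d = 0.5: 0.0625/1.0625 = 0.059

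Multiplying atanh of these by sqrt(197) = 14.04 gives 0.309 and 0.826. The two-sided rejection probabilities are:

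- d = 0.3: Phi(−1.651) + Phi(−2.269) = 0.061
- d = 0.5: Phi(−1.134) + Phi(−2.786) = 0.131

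A simulation of 40,000 replicates under the same assumptions (Monte Carlo standard error 0.001 to 0.002) agrees. It also covers other ways of handling condition:

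| Shift (attention, expectancy), SD | Condition never in | Always in | In only if P < 0.05 | One arm only |
|---|---|---|---|---|
| 0, 0.5 | 0.050 | 0.051 | 0.051 | 0.052 |
| 0.3, 0.3 | 0.061 | 0.048 | 0.050 | 0.050 |
| 0.5, 0.5 | 0.129 | 0.050 | 0.051 | 0.051 |

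The first row shows that there is no inflation if the ads do not shift attention.

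**Step 4. Price of adjusting.** One further degree of freedom gives tanh(2.802/sqrt(196)) = 0.198, still 0.20 to two decimals.

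**The case against.** **The label may be explained elsewhere.** Figure 2 and the opening part of the document are not available. This stands, so one can say that the label does not match the described conditions, not that the plan never defines it. A definition there would still have to be reconciled with the names in Primary Measures.

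**The label may come from a design with a non-smoking film.** Restricting an analysis of attention to smoking cues to those who saw such cues would then be sensible. The available text describes no such group. If one exists, the wording proposed below must be adapted.

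**A one-arm analysis is not an error.** Agreed. A within-arm association is a legitimate estimand and is free of confounding by ad condition. The available text sets no power target for it, so lower precision breaches nothing. What remains is that the arm is not identified.

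**Reading 2 does little harm.** Largely agreed. If condition is a candidate under the plan's own P < 0.05 rule, the false-positive rate stays at about 5%. The first ad break comes at 5 minutes of a 15-minute clip, so attention scored before then cannot be shifted by the ads, and the text does not say which segments are scored.

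A reader might also infer two stronger points that the documents do not support:

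- *The plan flatly contradicts its full-sample sentence.* That needs the one-arm reading and also a literal reading of a sentence that may mean only overall and by sex. A specific sentence would also ordinarily override a general one. The tension is secondary.
- *The plan's test for sex differences in the attention association loses power.* The Wald test is on "conduct formal tests for interactions using a Wald Test on sex by exposure multiplicative interaction terms in full models". The text uses exposure for ads and for long-term movie smoking, not for attention scores, so that test may not cover attention at all.

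**Conclusion.** The point holds as a mismatch between a stated analysis population and the design described. The second regression cannot be carried out as written without guessing whom it includes.

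Its size depends on the reading. If one ad arm is meant, the detectable correlation is 0.28 instead of 0.20 and power at 0.20 is about 51% instead of 81%. These figures are illustrations that rest on the assumptions in step 2, none of which except the 200 comes from the documents. If everyone is meant, no participants are lost. The false-positive rate is 6% when the ads shift both variables by 0.3 SD and condition is omitted. The 13% at 0.5 SD is a worst case, and nothing in the documents supports shifts of that size.

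It would be wrong to infer that the trial's main comparison is compromised. The randomised comparison of expectancy by advertising condition does not use this population and is unaffected. The plan should be corrected before analysis, but this is a repair of wording and model specification, not a flaw in the design.

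**What to change.** State the population for the second regression with the condition names used in Primary Measures.

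If a one-arm estimand is intended, name the arm and state it as an exception to the full-sample sentence. Otherwise, wording along these lines would serve:

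> In all randomised participants with eye-tracking data, from both the ENDS ad and the control ad conditions, the post-exposure expectancy score will be regressed on attention and advertising condition. Condition stays in the model whatever its P value. Arm-specific slopes and the attention-by-condition interaction are exploratory.

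The plan should also say whether the full-sample sentence means overall and by sex.

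The cost is SAP wording and one degree of freedom, with no new data. The downside is that the main model assumes a common slope, and the exploratory interaction has low power to check it. With 100 per arm it detects a Fisher-z difference of 2.802 × sqrt(2/97) = 0.40, for example r = 0 against r = 0.38. Under 2:1 allocation the figure is 2.802 × sqrt(1/64 + 1/130) = 0.43.
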